5.5 Disease Assessment

Disease response will be obtained by the assessment of PSA at enrollment and at the time the patient comes off study. PSA will not be repeated at these times if it has been done within 2 weeks for clinical care. Imaging studies will be done only if clinically indicated and/or at the discretion of the subject's primary oncologist.

5.6 Toxicity Assessment

See [Section 7](#).

5.7 Schedule of Assessments

See [Appendix A](#).

5.8 Correlative Studies

Samples will be processed and stored locally in [name] lab in HO334. The trial will be carried out at MUSC and one other cancer center (to be determined). Correlative studies will be done and will be exchanged between participating institutions. Samples may be stored for future use.

6 STUDY DRUG INFORMATION - CHITOSAN

6.1 Agent Description.

Chitosan is a natural polycationic linear polysaccharide derived from partial deacetylation of chitin. It is the structural element in the shell of insects, certain shellfish, and the cell walls of fungi. After cellulose, it is the most abundant natural polysaccharide. Chitosan is made up of B-(1-4)-lined D-glucosamine and N-acetyl-D-glucosamine randomly distributed within the polymer.

This study will use LipoSan Ultra® brand of chitosan, to reduce blood and tissue levels of advanced glycation endproducts, as an adjunct to prostate cancer treatment. LipoSan Ultra® is a proprietary combination of chitosan and succinic acid. Its composition and manufacture is covered by US Patent No. 6,130,321; it is manufactured in the US by Swanson Health. LipoSan Ultra® has also been awarded a certificate of compliance with the Tún Standards for Certified Natural Products.

6.1.1 Supply

Chitosan will be provided in 500mg capsules. Chitosan will be stored at the investigational pharmacy located at each participating center. Chitosan will be distributed by the investigational pharmacy at each participating center. Due to COVID-19 restrictions Chitosan can also be mailed to the subject directly. It will be purchased from an external supplier and repackaged by the investigational pharmacy at each participating center. The packaging will include the label information required per 21 CFR part 312.

6.1.2 Storage.

The capsules should be stored at a controlled room temperature, with excursions to 15-30°C (59-86°F) permitted. All capsules should be kept in a secured storage area.

6.1.3 Administration.

See section 4.2 for chitosan administration instructions.

6.1.4 Known Potential Toxicities.

Patients with allergies to any shellfish should not take Chitosan as it can cause anaphylactic shock. Known toxicities of chitosan include included flatulence, increased stool bulkiness, bloating, mild nausea, and heartburn. Chitosan may interfere with how your body absorbs some medications, including certain beta blockers (propranolol), blood thinners (warfarin), diuretics (thiazides), cholesterol medications (zetia), diabetes medications (rosiglitazone), and antibiotics (ciprofloxacin). It is important that you take the study drugs as instructed by the study doctor to avoid any possible drug interactions.

7 RISKS AND BENEFITS

7.1 Potential Risks

See Section 6.1.4 for the potential risks of Chitosan.

- The physical risk to participants is minimal. Venipuncture may produce momentary discomfort from needle stick, bruising or infection. Fainting could occur. The volume of blood removed is insignificant.
- The risk of distress from inappropriate release of PHI is low, due to the plan for de-identification of clinical data, as well as the likelihood that the clinical collaborators will already be involved in the subjects' health care.

7.2 Protection Against Risk

- The proposed procedures are inherently of low physical risk. We believe the psychological risks are also extremely low, since the investigators will already be treating the patients.
- We do not anticipate the occurrence of adverse events requiring treatment, or necessitating a data and safety monitoring board.
- Samples and results will be coded through the assignment of a unique study number to subject. Study labs will not have access to the ID log that contains the subject identifier. It will be stored separately from the research data.

7.3 Potential benefits of the proposed research to the subjects and others

There is no direct benefit to the participating subjects. Society may benefit if the new assays provide greater certainty about the diagnosis and behavior cancer and its response to therapy. In view of the extremely low risk of this study, the risk:benefit ratio seems favorable.

7.4 Withdrawal of subjects

Subjects can withdrawal from the study at any time without if affecting their regular care. The subject can be removed from study at any time if it is determined it is not in the subject's best interest to remain on the trial, the subject is non-compliant, or if the study is closed.

If the subject withdraws or is withdrawn from the study, the study team will stop collecting new information and specimen from the subject, but information and specimens already collected may still be used in the data analysis.

8 ADVERSE EVENTS

8.1 Definitions

Adverse Events (AE). An AE is defined as any untoward medical occurrence in a patient or clinical investigation subject administered a pharmaceutical product and that does not necessarily have to have a causal relationship with this treatment. An AE can therefore be any unfavorable and unintended sign (including an abnormal laboratory finding), symptom, or disease temporally associated with the use of the study drugs, whether or not is it causally related. During clinical trials, adverse events can be spontaneously reported or elicited during open-ended questioning, examination, or evaluation of a subject. (In order to prevent reporting bias, subjects should not be questioned regarding the specific occurrence of one or more adverse events.)

Adverse events will be named and graded using CTCAE v 5.0 and will be recorded prospectively during the study and entered into the REDCap database. Adverse events will be reported from the first day of study intervention until the last day of study intervention.

Serious Adverse Event (SAE). An SAE is any untoward medical occurrence that at any dose:

- results in death,
- is life-threatening (defined as an event in which the patient was at risk of death at the time of the event; it does not refer to an event which hypothetically might have caused death if it were more severe),
- requires inpatient hospitalization or causes prolongation of existing hospitalization,
- results in persistent or significant disability/incapacity,
- is a congenital anomaly/birth defect,
- results in the development of drug dependency or drug abuse,
- is an important medical event (defined as a medical event(s) that may not be immediately life-threatening or result in death or hospitalization but, based upon appropriate medical and scientific judgment, may jeopardize the patient or may require intervention (e.g., medical, surgical) to prevent one of the other serious outcomes listed in the definition above.) Examples of such events include, but are not limited to, intensive treatment in an emergency room or at home for allergic bronchospasm; blood dyscrasias or convulsions that do not result in hospitalization.

8.2 Reporting of SAEs

Following the subject's registration, all SAEs should be collected and reported, including those thought to be associated with clinical trial procedures. SAE terminology and severity grading will

be based on CTCAEv4. The following categories and definitions of causal relationship to study drug should be used:

- Definitely related: An adverse event occurring in a plausible time relationship to drug administration, and which cannot be explained by concurrent disease or other drugs or chemicals. The response to withdrawal of the drug should be clinically plausible. The event must be definite pharmacologically or phenomenologically, using a satisfactory rechallenge procedure if necessary and feasible.
- Possibly related: An adverse event with a reasonable time sequence to administration of the drug, but which could also be explained by concurrent disease or other drugs or chemicals. Information on drug withdrawal may be lacking or unclear.
- Not related: An adverse event with a temporal relationship to drug administration which makes a causal relationship improbable, and in which other drugs, chemicals or underlying diseases provide plausible explanations.

Adverse events classified as “serious” require expeditious handling and reporting to the coordinating center and Sponsor-Investigator. SAEs must be reported to all of these entities within 24hrs of becoming aware of the event, *whether or not the event is related to the study drugs or procedures*. If only limited information is initially available, follow-up reports are required. The original SAE form must be kept on file at the study site.

SAEs should be reported on the 102898 SAE eCRF via REDCap at redcap.musc.edu. The coordinating center will be responsible for submission to the Sponsor-Investigator, HCC-DSMC and FDA as applicable. SAEs should be reported to the site’s IRB per institutional standards.

The site should receive confirmation from MUSC that the SAE report was received. If not, please contact the SIS Unit immediately.

Collection of complete information concerning SAEs is extremely important. Thus, follow-up information which becomes available as the SAE evolves, as well as supporting documentation (e.g., hospital discharge summaries and autopsy reports), should be collected subsequently, if not available at the time of the initial report, and immediately sent using the same procedure as the initial SAE report.

AEs should be followed to resolution or stabilization, and reported as SAEs if they become serious. This also applies to subjects experiencing AEs that cause interruption or discontinuation of study

drugs, or those experiencing AEs that are present at the end of their participation in the study; such subjects should receive post-treatment follow-up as appropriate. All SAEs must be collected which occur within 30 days of discontinuation of dosing or completion of the patient's participation in the study if the last scheduled visit occurs at a later time.

8.3 Unanticipated Adverse Device Effects

An unanticipated adverse device effect (UADE) is any serious adverse effect on health or safety, any life-threatening problem or death caused by, or associated with a device, if that effect, problem, or death was not previously identified in nature, severity, or degree of incidence in the application; or any other unanticipated serious problem associated with a device that relates to the rights, safety, or welfare of subjects.

UADEs will be reported to the FDA by the PI within 10 working days of being notified of the event.

9 DATA SAFETY MONITORING

9.1 Responsible Individuals and Organizations.

The Principal Investigator will be responsible for monitoring the safety and efficacy of the trial, executing the DSM plan, and complying with all reporting requirements. This will be accomplished under the oversight of the HCC DSMC.

The HCC DSMC is responsible for monitoring data quality and patient safety for all interventional IITs at HCC. The HCC DSMC will have oversight of this protocol. The HCC DSMC will meet at a minimum on an annual basis to discuss the investigator-initiated trial. Also, the IIT will be audited by the DSMC auditor or external agency at least once a year.

The DSMC reviews all IRB reportable serious adverse events, monitoring/ auditing reports, and protocol deviations and has the authority to recommend closure and/or suspension for trials on which there are safety or trial conduct issues and may submit recommendations for corrective actions. The DSMC recommendations for modifications to the trial (if requested) are forwarded to the principal investigator. The principal investigator is notified of this recommendation in order that he/she may alert all investigators involved in the trial with regard to the potential action. At this time the principal investigators may submit to the DSMC additional information that could affect the Committee's decision.

All IRB reportable serious adverse events, monitoring/ auditing reports will be reviewed by the HCC DSMC for review during the DSMC monthly meetings. The SIS Unit will forward the event report to the HCC DSMC so that the information can be reviewed at the next available DSMB meeting. During the DSMB review, the DSMB can make recommendations for any further study action. The SIS Unit will maintain a copy of the DSMB approval letters for each event review within this study's central file.

9.2 Data Collection

Electronic CRF's will be provided for the recording of data and reporting that requires expedited review, such as SAE submissions. All data should be substantiated by clinical source documents organized within a patient research record. ICH Good Clinical Practices are to be followed. Data submission guidelines are outlined in the 102508 Operations Manual.

Electronic data for on study and follow-up patient data is submitted via the electronic system called REDCap. REDCap is managed from MUSC as a consortium partner under their CTSA. REDCap CRF is a secure, Web-based application designed to capture and manage research study data.

The system has been reviewed for 21CFR Part 11 compliance and has been deemed "21CFR 11 Capable." Users of the REDCap system are limited to members of the IRB approved research team who are delegated data management responsibilities, typically the study coordinator and data manager.

9.3 Food and Drug Administration Review

An IND for chitosan will be submitted to the FDA in accordance with 21 CFR 312.

Review of the AGE Reader by the Food and Drug Administration is not indicated as this study does not meet the significant risk device criteria under 21 CFR 812.3(m). This study will follow the abbreviated reporting requirements found under 21CFR 812.2(b), which includes that the device will be labeled in accordance with 21CFR 812.5 (Caution – investigational device. Limited by Federal lab to investigational use). The label or other labeling shall describe all relevant contraindications, hazards, adverse effects, interfering substances or devices, warnings and precautions.

10 STATISTICAL METHODS AND POWER ANALYSIS

10.1 Escalation Design

The investigators will use a 3+3 design for assignment to cohorts. The cohorts are shown in Table 3. An initial 3 subjects will be enrolled at dose level 1. Dose-limiting toxicities (DLT) will be defined only in the first 28 days of therapy. If there are no DLTs after the final patient has been treated for 28 days, then the next cohort will be enrolled in dose level 2, and so forth. If a DLT occurs, then 3 more subjects will be enrolled into that cohort. If two DLTs occur in the first 3 patients in a dose level, then dose will be de-escalated and 3 additional patients will be enrolled in the lower dose

Dose Level	Chitosan	number
-1	500mg QD	3 (+3)
1	500mg BID	3 (+3)
2	1000mg BID	3 (+3)
3	1500mg BID	3 (+3)
4	2000mg BID	3 (+3) +30

level unless 6 have already been treated at that dose level. The MTD will be defined as the dose at which no more than 1 out of 6 subjects experiences a DLT.

Definition of DLT:

- Grade 3 or higher hypophosphatemia
- Grade 3 or higher of any of the following toxicities, that the investigator deems related to chitosan, that do not improve or resolve within 7 days of onset: flatulence, increased stool bulkiness, bloating, nausea, heartburn

10.2 Expansion Cohort Design and Statistical Analysis.

Once the MTD is established, 27 additional subjects will be recruited at that dose level to better define toxicity and changes in AGEs. The maximum number of patients that can be accrued is 54. The primary measure of change in AGE is defined as a binary indicator of a 30% or greater decrease in plasma total AGE level between baseline and day 85 specimens. The proportion of patients with a 30% or greater decrease will be calculated with its exact 95% confidence interval. An exact binomial test will be based on a null hypothesized true proportion of 0.25 (i.e., 25% of patients have a $\geq 30\%$ reduction in AGE levels) which is too low to be of further interest. With an alternative of 0.50 and 33 patients, assuming a 1-sided alpha of 0.05, the power is 0.88. Graphical displays will be made to demonstrate patterns in AGE between baseline and day 85. The following analyses will be performed, and then data will be stratified by race, and analyses repeated to evaluate differences by race. Summary statistics (mean change between timepoints, standard deviations, medians) will be reported. Scatterplots and paired t-tests will be used to compare the mean change between baseline and day 85 with a 2-sided alpha of 0.05 for changes in AGE levels and changes in other variables of interest (e.g. race, BMI). Linear regression will be used to evaluate associations between continuous variables and changes in AGE levels with changes in AGE levels as the outcome. Transformations will be taken as appropriate and residual plots will be examined to evaluate assumptions of linear regression model. The investigators will add baseline levels of clinical parameters in the linear regression model to account for starting levels. Regression coefficients will be evaluated in terms of clinical effect size and statistical significance. Model results will be reported with 95% confidence intervals.

REFERENCES

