Chitosan is a linear polysaccharide composed of randomly distributed $\beta(1\rightarrow4)$ -linked D-glucosamine (deacetylated unit) and *N*-acetyl-D-glucosamine (acetylated unit). It is made by treating the chitin shells of shrimp and other crustaceans with an alkaline substance such as sodium hydroxide. Chitosan can also be recovered commercially from the stems of mushrooms. Like sevelamer, chitosan is also a polymer decorated with free amino groups that become partially protonated at the intestinal pH. It can bind phosphorus and other anions, as well as AGEs. In contrast to sevelamer, chitosan is derived from food sources and is safe and inexpensive. These parallels suggest that chitosan could be a clinically useful AGE-lowering agent.

Several studies in mice and humans implicate carbonyl stress from methylglyoxal (MG)-derived AGEs in diabetic nephropathy (45,46). Chitosan directly binds MG-derived AGEs *in vitro* and lowers serum and tissue levels of AGEs in mouse models (46). Furthermore chitosan treatment reduced AGE-related nephropathy in mice, both histologically and clinically. A small clinical trial of chitosan administration to chronic dialysis patients demonstrated an improvement in several biochemical parameters of nephropathy with the treatment (47). However no studies to date have demonstrated that chitosan can reduce either serum or tissue levels of AGEs in humans with AGE-related diseases. Similarly there are no clear data as to the *in vivo* mechanism by which chitosan reduces AGEs in animal models.

1.6.3 Biodistribution of oral chitosan.

The systemic absorption and distribution of chitosan following oral exposure are likely influenced by the molecular weight of the polymer. The effect of molecular weight on chitosan absorption has been evaluated in male Sprague Dawley rats (48). Oral gavage administration of chitosan with molecular weights of 3.8, 7.5, 13, 22, or 230kDa resulted in maximum plasma

chitosan concentrations (C_{max}) of 20.23, 9.30, 5.86, 4.32, or less than 0.5 µg/mL, respectively. The results of this study suggest that the absorption of chitosan from the gastrointestinal tract following oral exposure is inversely related to chitosan molecular weight, as there is likely low bioavailability associated with the higher molecular weight chitosan polymers.

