3 SUBJECT SELECTION

3.1 Inclusion Criteria

1. Confirmation of adenocarcinoma of the prostate that is documented by one of the following: pathology report or clinic note with documented history of prostate cancer.
2. Subjects must be receiving ADT with a GnRH agonist or antagonist, with or without an anti-androgen or testosterone synthesis inhibitor. The current testosterone level must be documented to be $<50\text{ng/dL}$ at enrollment. Subjects whose ADT is interrupted may enroll or continue on study as long as the testosterone is documented to remain $<50\text{ng/dL}$ for the entire duration of study participation. Subjects who have undergone orchiectomy are also eligible.
3. Subjects must have adequate hematologic, renal, and hepatic function at baseline, as follows:
 - Hematology parameters: ANC $>1000/\text{mcL}$, platelets $>100,000/\text{mcL}$, Hgb $>8.0\text{gm/dL}$

- Renal Function: eGFR of ≥ 45 mls/min using Cockcroft and Gault formula
 - Liver Function: Total bilirubin \leq ULN, AST and ALT <1.5 x ULN
4. Able to swallow and retain oral medication
 5. ECOG performance status of 0 – 2
 6. Ability to sign written informed consent
 7. Testosterone level <50 ng/dL at time of enrollment.
 8. Age 18 or older.
 9. May have had prior radiation therapy, surgery, or cryoablation for primary prostate cancer
 10. May have had prior cytotoxic chemotherapy for metastatic prostate cancer, prior treatment with genomically-targeted agents, or Provenge

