5.2 Assessments and Procedures

The following clinical assessments are made at the time subjects are screened for the trial. Some of these may need to be repeated prior to day 1; see Appendix A for more details regarding the schedule of procedures and assessments.

- A full medical history and physical examination to review patient medical history, medication list, overall health and any side effects they may be experiencing. Medical history will include:
 - Extent of cancer to include metastatic disease
 - Concomitant medications
 - current ADT therapy
- Height, weight
- CBCD
- CMP (sodium, potassium, chloride, bicarbonate, BUN, creatinine, glucose, albumin, alkaline phosphatase, AST, ALT, calcium)
- PSA, testosterone
- Research blood, urine, and stool samples as outlined (see Appendix A)
- 24hr food intake recall questionnaire
- Quality of life questionnaires (FACT-P and AUA; see Appendices B, C)
- Measurement of tissue AGE level by skin autofluorescence using the AGE Reader device.

On day 29 of the study, a phone call will be made to the patient to assess any possible adverse events (AEs).

The following clinical assessments are made on day 85/End of study

- Interim medical history and focused physical exam to review:
 - Changes to the patient's medical history,
 - Changes to ADT

- Changes to familial history of diabetes
- Change to medication list
- Overall health and any side effects they may be experiencing.
- Height, weight
- CBCD
- CMP (sodium, potassium, chloride, bicarbonate, BUN, creatinine, glucose, albumin, alkaline phosphatase, AST, ALT, calcium)
- PSA
- Research blood and urine samples as outlined (see Appendix A)
- 24hr food intake recall questionnaire
- Measurement of tissue AGE level by skin autofluorescence using the AGE Reader device.
- Day 85: Quality of life questionnaires (FACT-P and AUA; see Appendices B, C)

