APPENDIX A. SCHEDULE OF PROCEDURES AND ASSESSMENTS

Study Activity	Screen ^c	Day 1 ^c	Day 14 ^g	Day 29	Day 57 ^g	Day 85/ End of study ^{a, d}	Specimen	
Demographics	X							
Full Physical Exam,	X							
Focused Physical Exam,		X				X		
Medical History to include: 
 • Duration of ADT • Extent of cancer • Personal history of diabetes mellitus • Current medications 	X	X						
Interim Medical History		X				X		
Anthropometric Measurements (height, weight)	X	X				X		
CBCD	X	X				X		
CMP (fasting) ^g	X	X				X		
Phosphorus	X	X				X		
PSA	X	X				X		
Assessment of toxicity		X	X ^g	X ^g	X ^g	X		
testosterone	X	X				X		
Chitosan			X-----X					
Drug diary review ^e						X		
Informed consent	X							
Insulin Resistance (HOMA-IR)		X ^f				X	Plasma ^b	
CRP, AGE species and precursors		X ^f				X	Serum ^b	
RedOx status (ORP, reduced glutathione)		X ^f				X	Plasma ^b	
RAGE, TLR expression, signaling		X ^f				X	Whole blood ^b	
Microbiome profiling		X ^f				X	Stool	
AGE species		X ^f				X	Urine ⁱ	
Tissue AGE level by autofluorescence		X				X		
Food Recall Dietary AGE content ^h		X ^f				X		
QOL (FACT-P and AUA)		X ^f				X		

- All days are +/- 5 days
- 2x7mL EDTA blood (=plasma), 2x7mL clot tube (=serum), 1x7mL sodium heparin tube (=whole blood).
- Screening assessments to be done within 28 days of registration. Screening assessments may be used for the day 1 assessments if they were completed within 28 days of day 1. The CMP used for eligibility confirmation does not have to be fasting, but a fasting CMP will need to be collected prior to day 1 drug administration. Fasting is defined as nothing containing calories since the previous midnight.
- If the subject goes off study less than 2 weeks after start of dosing, "end of study" labs and questionnaires will not be done.
- The drug diary will be given to each subject for completion during the study.
- Research procedures (excluding informed consent) may be done at any point after informed consent and prior to first dose of drug (on day 1). Research blood, urine and stool samples will be taken to the participating research lab(s) for processing.

NCT # NCT03712371

CTO # 102928

Version Date: 09/09/2020

- g) On day 14, day 29, and day 57 (+/- 5 days), compliance and adverse events will be assessed via phone using the phone contact guide in appendix D.
- h) Food recall using the NCI quick food scan and the NIH's "Eating at America's Table Study" Quick food scan.

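### Phosphorus is a DLT analyte with no entry limit and no baseline rule, so an unchanged pre-existing low value can be counted as a DLT

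*Combined protocol and SAP*

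**What the plan says.** - **DLT definition (10.1).** There are two bullets. The first is "Grade 3 or higher hypophosphatemia", with no further condition. The second covers gastrointestinal events of the same grade and counts only those "that the investigator deems related to chitosan, that do not improve or resolve within 7 days of onset". DLTs are counted in the first 28 days of therapy.
- **Escalation rule (2.2, 10.1).** One DLT adds 3 subjects to the cohort. Two in the first 3 lead to de-escalation. The MTD allows at most 1 DLT in 6.
- **Reason to watch phosphorus (1.6.2).** Of chitosan: "It can bind phosphorus and other anions, as well as AGEs".
- **Eligibility (3.1, 3.2).** Inclusion 3 opens "Subjects must have adequate hematologic, renal, and hepatic function at baseline, as follows" and then limits ANC, platelets, hemoglobin, eGFR, bilirubin, AST and ALT. Neither the inclusion nor the exclusion criteria mention phosphorus.
- **Sampling (Appendix A).** Phosphorus is scheduled at Screen, Day 1 and Day 85/End of study. Footnote c adds: "Screening assessments may be used for the day 1 assessments if they were completed within 28 days of day 1". For Days 14, 29 and 57, footnote g says "compliance and adverse events will be assessed via phone using the phone contact guide in appendix D".
- **Adverse event definition (8.1).** An abnormal laboratory finding qualifies whatever its cause. Worsening from baseline is not required.

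**The concern.** A toxicity endpoint should record what happens after dosing. Here the laboratory DLT is defined by an absolute grade, entry does not exclude subjects already at that grade, and the general adverse event definition supplies no baseline rule. A man who enters at grade 3 meets the DLT wording as soon as a value in the window is looked at, even if chitosan has done nothing. The plan does not tell the investigator how to count him.

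The primary objective, the MTD, is decided by one or two events in 3 to 6 subjects, so a single misattributed event matters. It costs 3 more subjects and a further 28-day wait, and it removes the margin for a real event at that level. There is also a safety side: a man at that grade would receive a phosphorus-binding agent although his result was available before the first dose.

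**Working it through.** The plan states no figure for this risk, so there is none to reproduce. The check sizes the consequence of the wording.

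**Inputs from the plan:** cohorts of 3 (+3), numbered levels 1 to 4, at most 1 DLT in 6 (10.1).

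**Assumptions, not in the documents:**
- *q* is the share of entrants already at DLT grade.
- *p* is the true drug DLT rate, taken as equal at all levels.
- Every pre-existing case is measured in the window and counted.
- A level passes with 0/3, or with 1/3 followed by 0/3.

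**Step 1. One case alone.** 1/3 leads to 6 subjects, and 1/6 still meets the MTD rule. A level fails only with a second DLT.

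**Step 2. Background only (p = 0).**
- At least one counted case in a cohort of 3: 1 − (1 − q)³
- Level passes: P = (1 − q)³ + 3q(1 − q)² × (1 − q)³
- MTD below level 4: 1 − P⁴

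Worked for q = 5%: 0.95³ = 0.8574; 3 × 0.05 × 0.95² = 0.1354; P = 0.8574 + 0.1354 × 0.8574 = 0.9734; 1 − P⁴ = 0.102.

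| q | At least one in a cohort of 3 | A given level fails | MTD below level 4 |
|---|---|---|---|
| 1% | 3.0% | 0.1% | 0.5% |
| 2% | 5.9% | 0.5% | 1.8% |
| 5% | 14.3% | 2.7% | 10.2% |
| 10% | 27.1% | 9.4% | 32.6% |

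The second column is almost entirely single cases, which expand the cohort. Two or more in the first 3 make up only 0.03%, 0.12% and 0.73% at q = 1%, 2% and 5%.

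**Step 3. Background on top of real toxicity.** Replace q by t = 1 − (1 − p)(1 − q). With p = 5%, the chance of an MTD below level 4 is 10.2% at q = 0, 18.0% at q = 2% (t = 0.069) and 31.4% at q = 5% (t = 0.0975).

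**Step 4. Detection.** For a man who stays on study, Appendix A has no phosphorus draw between Day 1 and Day 85. A counted value must therefore be the Day 1 value read literally, or an unscheduled draw. A man who leaves after two weeks but before day 28 could have end-of-study labs inside the window (footnote d). Incomplete detection scales q down. For example, if q = 5% and 20% of men had a draw in the window (both assumed), the effective q is 0.05 × 0.20 = 1%, and the background-only chance of an MTD below level 4 falls from 10.2% to 0.5%.

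**The case against.** The strongest objection is that the plan gives this event little opportunity to occur. The Day 1 value may be the screening value and naturally serves as the baseline; counting it as a toxicity is a strained reading. After that, Days 14 and 29 are telephone contacts. On this schedule a true hypophosphatemia DLT is more likely to be missed than a false one counted, which would bias the MTD upward. This stands. It limits the size of the problem but does not repair the definition, and the missing baseline rule would matter more if in-window sampling were added.

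Entry is also not wholly unguarded. Exclusion 3 removes men with a history of malabsorption, and exclusion 5 removes users of sevelamer, which section 1.6.1 describes as a phosphorus-lowering drug. These reduce q but set no limit.

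A reader comparing the two DLT bullets might infer that the missing relatedness condition is itself an error. The documents do not support that. For an agent the protocol describes as a phosphorus binder, counting every such event whatever the attribution is a defensible, conservative choice.

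**Conclusion.** The gap is real and its effect on the MTD is modest. No criterion limits phosphorus, and the DLT wording needs no change from baseline, so a man already at DLT grade is eligible and can be counted. With no drug toxicity and q of 1%, 2% or 5%, the chance of at least one such case in a given cohort of 3 is at most 3.0%, 5.9% or 14.3%. The chance of an MTD below level 4 is at most about 0.5%, 1.8% or 10.2%. All of this rests on an assumed q and full detection. Real toxicity at the same level makes a counted background case more costly.

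Three stronger readings do not hold:
- *That one pre-existing value shifts the MTD.* It does not, because 1 in 6 still qualifies.
- *That the chance of at least one case among 12 subjects, 1 − (1 − q)¹² = 11.4%, 21.5% or 46.0%, is the chance of a wrong MTD.* It is only the chance that some cohort is disturbed, again under full detection.
- *That any low phosphorus at entry counts.* Only grade 3 or higher does, and the documents give neither its prevalence nor the grade cut-offs.

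**What to change.** 1. **Section 3.1:** add a phosphorus entry criterion that uses the screening value already drawn. The sponsor sets the threshold.
2. **Section 10.1:** word the first DLT bullet as worsening to grade 3 or higher from the subject's own pre-dose value. No relatedness condition is needed. Name the grading version, since 8.1 cites CTCAE v5.0, 8.2 cites v4 and 10.1 cites none.
3. **Appendix A and 5.2:** reconcile the hypophosphatemia DLT with the schedule, which has no routine phosphorus draw after Day 1 within the 28-day window. The laboratory lists in 5.2 omit phosphorus altogether.

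Items 1 and 2 are wording only and need no new sample. The cost is that a few screened men with low phosphorus become ineligible. The cost of item 3 depends on how the sponsor resolves it.

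A separate, minor reconciliation: inclusion 3 sets a total bilirubin limit, but the itemized CMP in 5.2 leaves bilirubin out and Appendix A has no row for it. This has no bearing on DLTs or the MTD.
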